7.2 PLANNED ANALYSES

7.2.1 General considerations

With regards to each efficacy and safety endpoint, the term "baseline" refers to the last observed measurement prior to randomisation for all patients.

The statistical analysis will be based on the following populations:

The Randomised Set (RS) will consist of all randomised patients.

The Full Analysis Set (FAS) will consist of all randomised patients with at least one baseline and one post baseline assessment relating to the primary endpoint of interest - refer to [Section 2.1.2](#) for primary endpoints related to Part 1 and Part 2.

The Treated Set (TS) will consist of all patients who were randomised and, for patients in the alteplase groups, treated with at least one dose of trial drug.

Per Protocol Set (PPS) will consist of all patients in FAS who were without important protocol deviations (IPDs) for efficacy. The definition of IPDs will be specified in the Trial Statistical Analysis Plan (TSAP) but this PPS will only be determined for Part 2.

All endpoints will be presented for Parts 1 and Part 2 separately, and at the end of Part 2 most endpoints will additionally be pooled for descriptive purposes.

All analyses for all endpoints, both inferential and descriptive, including safety, will be performed on the NIV patient cohort, and the IMV patient cohort separately. This is in line with the statistical objectives of the study.

For selected endpoints, if homogeneity between the two patient cohorts is observed, combined treatment estimates will be determined using suitable meta-analysis techniques. These will be outlined in more detail in the Trial Statistical Analysis Plan.

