3. INTRODUCTION

As per ICH E9 ([1](#)), the purpose of this document is to provide a more technical and detailed elaboration of the principal features of the analysis, as described in the clinical trial protocol (CTP) Version 3 (c32434345-03, [2](#)). It will detail the procedures for executing the statistical analysis of the primary, all secondary endpoints, and other data, and will be limited to the analysis of Part 2 of BI trial 0135-0347.

CTP Version 3 is the updated CTP, following the interim results of Part 1. This TSAP assumes familiarity with CTP Version 3. In particular, the TSAP is based on the planned analysis specifications as written in CTP Version 3 Section 7 “Statistical Methods and Determination of Sample Size”. Therefore, TSAP readers may consult the CTP Version 3 for more background information on the study, e.g., on study objectives, study design and population, treatments, definition of measurements and variables, and planning of sample size and randomisation.

The NIV (non-invasive ventilation) patient cohort are those with a baseline WHO value of 6, and the IMV (invasive mechanical ventilation) patient cohort are those patients with a value of 7, 8 or 9 at baseline. All analyses will be performed within the NIV patient cohort as the main cohort for confirmatory purposes, and separately within the IMV patient cohort for exploratory purposes. This is consistent with the hierarchy testing approach following the primary and key secondary objectives of the statistical analysis, as outlined in CTP version 3 Section 7. Select analyses will be performed on the NIV and IMV cohorts pooled and the extent of the analyses will depend on the homogeneity observed of the two groups.

A database snapshot will be made when all patients have completed the day 28 visit and when the data has been cleaned. At this point, all analyses outlined in this Trial Statistical Analysis Plan (TSAP) will be performed, except for all cause mortality (ACM) at day 90. This further endpoint will be available at a later timepoint. When this data is available, then another snapshot will be taken, the database will be locked, and this endpoint will be analysed.

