Based on the main estimand, the treatment effect will be estimated using the Cox proportional hazard model, containing only treatment in the model. The HR (95%CI) and p-value estimating the unadjusted treatment effect will be produced.

The effect of the subgroups in the NIV patient cohort, as outlined in [Section 6.4](#), related to the primary endpoint, main estimand, will be assessed descriptively and using Kaplan Meier estimates. Using the Cox proportional hazard model, hazard ratio estimates with 95% CI will be estimated from the model in two different methods:

- Firstly, in a model containing treatment, subgroup and the treatment * subgroup interaction.
- Secondly, in the model containing the default set of covariates as outlined in [Section 7.4.1](#) with this additional covariate added.

A covariate adjusted sensitivity analysis of the primary endpoint, main estimand, will be conducted, to determine the effect of the grouping of centres according to similar types of Standard of care. This will be the same analysis.

For the NIV and IMV cohorts pooled, the Cox proportional hazard model will be used, including the fixed effects for treatment (alteplase, SOC), baseline D-Dimer status (≥ 3 to < 5 , ≥ 5 -fold ULN), age and baseline ventilation status (NIV, IMV). From this model, the HR and 95% CI will be produced. In addition to this model, the interaction term for the baseline ventilation status and treatment will be included, and the p-value for this additional term will be used as a test of homogeneity. If the p-value is > 0.05 the it can be considered that the two groups are homogeneous, with respect to this primary endpoint.

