7.5.1.1 Primary analysis of the key secondary endpoints

The risk difference (RD) will be estimated between the two treatment arms using logistic regression. In addition to treatment, adjustment will be made for the default set of covariates, according to the NIV or IMV patient cohort as outlined in [Section 7](#). RD and CIs (95%) for the RD will be obtained using the Delta method and the average marginal effect (AME) method.

7.5.1.2 Sensitivity analysis, subgroup analysis, exploratory analysis of the key secondary endpoints

As sensitivity analysis for each of these binary efficacy endpoints, the unadjusted treatment estimates will be produced, using the same logistic regression model containing only treatment.

For the NIV and IMV cohorts pooled, the RD and 95% CI will be estimated between the two treatment arms using logistic regression, the Delta and the average marginal effect (AME) method. Adjustment will be made for treatment (alteplase, SOC), baseline D-Dimer status (≥ 3 to < 5 , ≥ 5 -fold ULN), age and baseline ventilation status (NIV, IMV). In addition to this model, the interaction term for the baseline ventilation status and treatment will be included, and the p-value for this additional term will be used as a test of homogeneity. If the p-value is > 0.05 the it can be considered that the two groups are homogeneous, with respect to these two key secondary efficacy endpoints.

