7.5.2 Other Secondary endpoints

Other secondary endpoints are defined in [Section 5.2.2](#). In all cases, standard descriptive statistics will be presented, whether the endpoint is binary or continuous.

Binary safety endpoint

For the binary safety endpoint MBE up to day 6, analysed on the TS, there will be no adjustment for covariates. Therefore, the RD will be the difference between the two incidences and the p-value and 95% CI will be determined using the Chan and Zhang exact method.

For the NIV and IMV cohorts pooled, the RD 95% CI will be estimated between the two treatment arms using the same approach as for the key secondary efficacy endpoints. However, for this pooled investigation of MBE up to day 6, the baseline D-Dimer status (≥ 3 to <5 , ≥ 5 -fold ULN) and age covariates will not be included in the model. The p-value for homogeneity will be determined similarly.

Continuous efficacy endpoints

The three other secondary endpoints which are continuous in nature will be analysed using a restricted maximum likelihood (REML) based ANCOVA comparing the outcome, by treatment. The ANCOVA model will be adjusted for the default set of covariates as outlined in [Section 7](#) for the respective NIV and IMV patient cohorts. The treatment difference with 95% CI and p-values will be presented.

For the continuous efficacy endpoints, number of OFDs at day 28, and number of days in hospital, there are not expected to be any missing values by definition and as outlined in [Section 5.2.2](#).

[figure not shown]
For the continuous efficacy endpoint change from baseline in the $\text{PaO}_2/\text{FiO}_2$ at day 6, the baseline $\text{PaO}_2/\text{FiO}_2$ will also be included in the model as covariate for adjustment. For patients that have died, or who have been discharged from hospital, the handling rules are as outlined in [Section 5.2.2](#). Note, there are expected to be very few deaths or hospital discharges prior to day 6.

In addition, subgroup analyses of this $\text{PaO}_2/\text{FiO}_2$ endpoint will be conducted in the NIV patient cohort only and using the subgroups as outlined in [Section 6.4](#). An ANCOVA model will contain the baseline $\text{PaO}_2/\text{FiO}_2$, the subgroup of interest and the interaction between subgroup and treatment.

As sensitivity analyses, the unadjusted treatment effects will be estimated, using the same approach as the main analysis, but with only treatment in the model.

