Within this section, all descriptive analyses will be performed on the NIV patient cohort, the IMV patient cohort and on the NIV and IMV cohorts pooled.

For the NIV and IMV cohorts pooled, the treatment difference and 95% CI will be estimated between the two treatment arms using a restricted maximum likelihood (REML) based ANCOVA comparing the outcome, by treatment. The ANCOVA model will be adjusted for treatment (alteplase, SOC), baseline D-Dimer status (≥ 3 to < 5 , ≥ 5 -fold ULN), age and baseline ventilation status (NIV, IMV). In addition to this model, the interaction term for the baseline ventilation status and treatment will be included, and the p-value for this additional term will be used as a test of homogeneity. If the p-value is > 0.05 the it can be considered that the two groups are homogeneous, with respect to these three other secondary efficacy endpoints.

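### The Part 2 SAP reads an interaction p-value above 0.05 as homogeneity of the NIV and IMV cohorts, although that test has 14-45% power if alteplase works in NIV (HR 2.0) and does nothing in IMV (exploratory analyses only)

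*SAP*

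**What the plan says.** **The rule.** In Part 2 SAP 7.4.2 the pooled Cox model is first fitted with treatment, D-dimer status, age and ventilation status, and gives a pooled HR with 95% CI. An interaction between ventilation status and treatment is then added, and "the p-value for this additional term will be used as a test of homogeneity". Above 0.05, "it can be considered that the two groups are homogeneous, with respect to this primary endpoint". SAP 7.5.1.2 repeats this for treatment failure and mortality ("it can be considered that the two groups are homogeneous, with respect to these two key secondary efficacy endpoints"), and 7.5.2 for the three continuous endpoints ("it can be considered that the two groups are homogeneous, with respect to these three other secondary efficacy endpoints"). For pooled major bleeding, 7.5.2 says only that "The p-value for homogeneity will be determined similarly"; no 0.05 rule is attached.

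**What is tied to homogeneity.** SAP section 3 says of the pooled analyses that "the extent of the analyses will depend on the homogeneity observed of the two groups". Protocol 7.2.1 says that, for selected endpoints, "if homogeneity between the two patient cohorts is observed, combined treatment estimates will be determined using suitable meta-analysis techniques", and adds: "These will be outlined in more detail in the Trial Statistical Analysis Plan". The protocol synopsis makes an overall meta-analytic estimate subject to the same condition and calls it exploratory.

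**Size of the IMV cohort.** The synopsis caps IMV at 50 patients, about 32 on alteplase and 16 on SOC. Protocol 7.5 limits sample size considerations to NIV. Neither document gives an IMV event rate, an IMV effect, a margin for homogeneity or a power for the interaction test.

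**The concern.** Failing to reject a difference supports sameness only if the test would probably have found a difference that matters. Here one side of the comparison has at most about 48 patients, and the test was not sized for this use. In the visible SAP text, p > 0.05 is the only definition of homogeneity, so it would naturally supply the condition that section 3 and protocol 7.2.1 leave open.

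At stake is what the report says about intubated patients. If alteplase helps NIV patients and does nothing in IMV patients, the pooled HR is still well above 1, because NIV events dominate it. A pre-specified statement that the cohorts are homogeneous would lend that pooled figure support that the IMV data do not give.

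**Working it through.** **Inputs.** NIV: 140 alteplase and 70 SOC, event rates about 50% and 30%, HR 2.0, two-sided alpha 5% (protocol 7.5). IMV: 32 and 16 (synopsis). Assumed, because the documents give no figure: IMV HR 1.0, with 8 to 24 IMV events as a plausible range and 48 (every planned patient) as a ceiling.

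**The plan's own figure.** NIV events = 0.5×140 + 0.3×70 = 91. With 2:1 allocation the information is 91×(2/3)×(1/3) = 20.22. Power = Φ(ln 2×√20.22 − 1.96) = Φ(3.117 − 1.96) = 87.6%, inside the stated 85% to 90%. The same inputs give 86.0% for treatment failure and 85.1% for mortality (85% stated).

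**Interaction test, primary endpoint.** Var(log HR) in a cohort with d events is 1/(d×2/9) = 4.5/d, so SE = √(4.5/91 + 4.5/d). Power = P(|Z + δ/SE| > 1.96), with δ = ln(2.0/1.0) = 0.693, or δ = ln(2.0/0.5) = 1.386 if alteplase harms IMV patients.

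| IMV events d | SE | Power, IMV HR 1.0 | Labelled homogeneous | Power, IMV HR 0.5 |
|---|---|---|---|---|
| 8 | 0.782 | 14% | 86% | 43% |
| 24 | 0.487 | 30% | 70% | 81% |
| 48 | 0.378 | 45% | 55% | 96% |

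**Checks on the IMV HR 1.0 column.**
- Taking the NIV variance from the planned event split (1/70 + 1/21) gives 14%, 28% and 42%.
- Simulation with exponential times, day-28 censoring and a Cox fit in each cohort (10,000 trials per case) gives 15.1%, 29.4% and 43.4%.
- With all 48 IMV events, raising NIV events to 150 gives 50%; an event in all 210 NIV patients gives 53%.
- About 383 IMV events would be needed for 80% power.

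**What the rule would pass.** Suppose the observed ratio of hazard ratios is 2.0. With 24 IMV events, z = 0.693/0.487 = 1.42, p = 0.15, 95% CI 0.77 to 5.19. With 48, z = 0.693/0.378 = 1.83, p = 0.067, CI 0.95 to 4.20. Both would be labelled homogeneous.

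**Pooled estimate when the true IMV HR is 1.0.** By event weighting, exp(ln 2×91/(91+d)) = 1.89, 1.73 and 1.57 at d = 8, 24 and 48.

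**Other endpoints.**
- Treatment failure, logit scale: the planned NIV effect is ln[(0.4/0.6)/(0.2/0.8)] = 0.981. With no IMV effect and assumed IMV rates of 30-70%, power is 26-29%.
- Mortality (25% against 9% in NIV), same IMV assumptions: 34-38%.
- Continuous endpoints, equal SDs assumed: SE = √(1/140 + 1/70 + 1/32 + 1/16) = 0.339 SD. An effect that the NIV cohort would detect with 80% or 90% power (0.410 or 0.475 SD) and that is absent in IMV gives 23% or 29%.

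**The case against.** The strongest objection is that little depends on the rule. The pooled models are fitted whatever the p-value, cohort-specific estimates are planned throughout, the combined estimate is labelled exploratory, and the confirmatory tests use NIV only. All of that stands, and it sets the limit of the point. It does not make the inference valid: the sentence is pre-specified, it covers six efficacy endpoints, and no other criterion is visible.

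Four stronger readings may tempt a reader; the documents support none of them.

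- *The rule threatens the main result.* It does not. Protocol 7.1 confines the hierarchy to the NIV cohort.
- *The p-value decides whether pooled estimates are produced.* The SAP never says so. It gives the pooled estimates without condition and does not name the p-value as the trigger for the protocol's meta-analysis. The link runs only through the word homogeneity in SAP section 3, protocol 7.2.1 and the synopsis. Some SAP sections are also redacted.
- *The test is blind to any difference.* It is not. An IMV HR of 0.5 would be found 81% of the time at 24 IMV events, though only 43% at 8.
- *The bleeding analysis breaks down if no IMV SOC patient bleeds.* SAP 7.5.2 points to the approach for the key secondary endpoints, so the test is identified, though not its Wald or likelihood-ratio form. A likelihood-ratio p-value exists with an empty cell (0.27 in a constructed table: NIV 14/140 against 2/70, IMV 5/32 against 0/16).

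It is also fair that the IMV inputs are chosen, not documented. At the planned 91 NIV events, however, an IMV HR of 1.0 leaves power below 50% for any event count up to 48.

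**Conclusion.** The point holds as a fault of inference in exploratory analyses. Three SAP sections allow the cohorts to be considered homogeneous on a test with 14% to 45% power against a true HR of 2.0 in NIV and 1.0 in IMV, so that label would follow 55% to 86% of the time. Power is 26-38% for the key secondary endpoints and 23-29% for the continuous ones.

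The figures rest on 91 NIV events (derived, not printed), an assumed null IMV effect, assumed IMV event counts and rates, and, for the continuous endpoints, equal SDs. They would be lower for a smaller difference between cohorts (7-9% at 8-24 events if the IMV HR is 1.5) and higher if alteplase harms IMV patients. The change should be made, but no confirmatory conclusion depends on it.

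**What to change.** - **SAP 7.4.2, 7.5.1.2 and 7.5.2:** delete the three sentences that equate p > 0.05 with homogeneity. Report the interaction estimate with 95% CI beside the NIV, IMV and pooled estimates, on the scale of the planned model: ratio of hazard ratios, ratio of odds ratios from the logistic model, difference in mean differences. State that no conclusion of homogeneity is drawn from the p-value.
- **Binary endpoints:** also show the cohort-specific risk differences, because the scales can disagree. The planned NIV odds ratio for treatment failure is (0.2/0.8)/(0.4/0.6) = 0.375. Applied to an assumed IMV SOC rate of 30%, it gives odds of 0.429×0.375 = 0.161, a rate of about 14% and a risk difference of about −16 points, against −20 in NIV.
- **Pooled major bleeding:** keep the planned analysis and draw no conclusion of homogeneity from its p-value.
- **SAP section 3:** replace the dependence on observed homogeneity with a statement that the pooled models listed in 7.4.2, 7.5.1.2 and 7.5.2 are always presented, as exploratory.
- **SAP section 4:** record the departure from the condition in protocol 7.2.1 and the synopsis.

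The cost is wording in four sections, one entry in section 4 and a few added table columns. The interaction estimates come from models already planned, and SAP 7.5.1.1 already gives risk differences by cohort. No new data are needed.

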7.5 SECONDARY ENDPOINTS

Within this section, all descriptive analyses will be performed on the NIV patient cohort, the IMV patient cohort and on the NIV and IMV cohorts pooled.

7.5.1 Key secondary endpoints

The two key secondary efficacy endpoints, outlined in [Section 5.2.1](#), are binary in nature and will be analysed on the FAS for both the NIV patient cohort and the IMV patient cohort.

7.5.1.1 Primary analysis of the key secondary endpoints

The risk difference (RD) will be estimated between the two treatment arms using logistic regression. In addition to treatment, adjustment will be made for the default set of covariates, according to the NIV or IMV patient cohort as outlined in [Section 7](#). RD and CIs (95%) for the RD will be obtained using the Delta method and the average marginal effect (AME) method.

7.5.1.2 Sensitivity analysis, subgroup analysis, exploratory analysis of the key secondary endpoints

As sensitivity analysis for each of these binary efficacy endpoints, the unadjusted treatment estimates will be produced, using the same logistic regression model containing only treatment.

For the NIV and IMV cohorts pooled, the RD and 95% CI will be estimated between the two treatment arms using logistic regression, the Delta and the average marginal effect (AME) method. Adjustment will be made for treatment (alteplase, SOC), baseline D-Dimer status (≥ 3 to < 5 , ≥ 5 -fold ULN), age and baseline ventilation status (NIV, IMV). In addition to this model, the interaction term for the baseline ventilation status and treatment will be included, and the p-value for this additional term will be used as a test of homogeneity. If the p-value is > 0.05 the it can be considered that the two groups are homogeneous, with respect to these two key secondary efficacy endpoints.

7.5.2 Other Secondary endpoints

Other secondary endpoints are defined in [Section 5.2.2](#). In all cases, standard descriptive statistics will be presented, whether the endpoint is binary or continuous.

Binary safety endpoint

For the binary safety endpoint MBE up to day 6, analysed on the TS, there will be no adjustment for covariates. Therefore, the RD will be the difference between the two incidences and the p-value and 95% CI will be determined using the Chan and Zhang exact method.

For the NIV and IMV cohorts pooled, the RD 95% CI will be estimated between the two treatment arms using the same approach as for the key secondary efficacy endpoints. However, for this pooled investigation of MBE up to day 6, the baseline D-Dimer status (≥ 3 to <5 , ≥ 5 -fold ULN) and age covariates will not be included in the model. The p-value for homogeneity will be determined similarly.

Continuous efficacy endpoints

The three other secondary endpoints which are continuous in nature will be analysed using a restricted maximum likelihood (REML) based ANCOVA comparing the outcome, by treatment. The ANCOVA model will be adjusted for the default set of covariates as outlined in [Section 7](#) for the respective NIV and IMV patient cohorts. The treatment difference with 95% CI and p-values will be presented.

For the continuous efficacy endpoints, number of OFDs at day 28, and number of days in hospital, there are not expected to be any missing values by definition and as outlined in [Section 5.2.2](#).

[figure not shown]
For the continuous efficacy endpoint change from baseline in the $\text{PaO}_2/\text{FiO}_2$ at day 6, the baseline $\text{PaO}_2/\text{FiO}_2$ will also be included in the model as covariate for adjustment. For patients that have died, or who have been discharged from hospital, the handling rules are as outlined in [Section 5.2.2](#). Note, there are expected to be very few deaths or hospital discharges prior to day 6.

In addition, subgroup analyses of this $\text{PaO}_2/\text{FiO}_2$ endpoint will be conducted in the NIV patient cohort only and using the subgroups as outlined in [Section 6.4](#). An ANCOVA model will contain the baseline $\text{PaO}_2/\text{FiO}_2$, the subgroup of interest and the interaction between subgroup and treatment.

As sensitivity analyses, the unadjusted treatment effects will be estimated, using the same approach as the main analysis, but with only treatment in the model.

Within this section, all descriptive analyses will be performed on the NIV patient cohort, the IMV patient cohort and on the NIV and IMV cohorts pooled.

For the NIV and IMV cohorts pooled, the treatment difference and 95% CI will be estimated between the two treatment arms using a restricted maximum likelihood (REML) based ANCOVA comparing the outcome, by treatment. The ANCOVA model will be adjusted for treatment (alteplase, SOC), baseline D-Dimer status (≥ 3 to < 5 , ≥ 5 -fold ULN), age and baseline ventilation status (NIV, IMV). In addition to this model, the interaction term for the baseline ventilation status and treatment will be included, and the p-value for this additional term will be used as a test of homogeneity. If the p-value is > 0.05 the it can be considered that the two groups are homogeneous, with respect to these three other secondary efficacy endpoints.

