Total number of patients randomised	
Part 1: approximately 60 patients
 
Part 2: approximately 260 patients, thereof 210 non-invasive mechanical ventilation (NIV) and up to 50 invasive mechanical ventilation (IMV) patients
 
Randomisation will be stratified by type of ventilation support (invasive mechanical / non-invasive)
 
Additionally in Part 2:
 
Randomisation will be stratified by D-Dimer levels (\geqULN to <5-fold ULN, versus \geq5-fold ULN)
 
Randomisation of IMV patients will be stopped when a maximum of 50 IMV patients have been randomized in Part 2.
 
Randomisation for the whole trial will be stopped when approximately 210 NIV patients have been randomized in Part 2, regardless of how many IMV patients have been randomised so far.

Number of patients on each treatment	
Part 1: approximately 20 patients in SOC arm and 20 patients in each treatment arm
 
Part 2: NIV patients: approximately 70 patients in SOC arm and 140 in treatment arm

Clinical Trial Protocol

Page 4 of 140

Proprietary confidential information © 2022 Boehringer Ingelheim International GmbH or one or more of its affiliated companies

	IMV patients: up to approximately 16 patients in SOC arm and 32 in treatment arm
Diagnosis	ARDS due to COVID-19

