The most common AEs by system organ class were: respiratory, thoracic and mediastinal disorders (alteplase 0.3/0.02 mg/kg: 7 patients/35.0%, alteplase 0.6/0.04 mg/kg: 12 patients/60.0%, SOC: 9 patients/40.9%), infections and infestations (9 patients/45.0%, 4 patients/20.0%, 11 patients/50.0%), and general disorders and administration site conditions (7 patients/35.0%, 7 patients/35.0%, 4 patients/18.2%).

Serious AEs reported for >2 patients in a treatment group were respiratory failure (alteplase 0.3/0.02 mg/kg: 2 patients/10.0%, alteplase 0.6/0.04 mg/kg: 0 patients, SOC: 6 patients/27.3%), pulmonary embolism (2 patients/10.0%, 3 patients/15.0%, 1 patient/4.5%), septic shock (1 patient/5.0%, 0 patients, 4 patients/18.2%), and epistaxis (3 patients/15.0%, 1 patient/5.0%, 0 patients).

Treatment-emergent bleeding events were more frequent in the alteplase treatment groups, both for any bleeding events and major bleeding events. Major bleeding events up to Day 6 were reported only in the alteplase treatment groups (1 patient in the 0.3/0.02 mg/kg dosing group and 4 patients in the 0.6/0.04 mg/kg dosing group). Most bleeding events until Day 12 were non-major (4 patients, alteplase 0.3/0.02 mg/kg; 9 patients, alteplase 0.6/0.04 mg/kg; 3 patients, SOC group). There were no fatal bleeding events.

The study results of Part 1 support the continuation of the study into Phase III (Part 2), implementing a comparison of the alteplase 0.6/0.04 mg/kg dose versus SOC alone.

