7.2.3 Secondary endpoint analyses

[figure not shown]
For the list of key secondary and secondary endpoints, refer to [Section 2.1.3](#). Summary statistics will be presented for each endpoint, and at each visit if appropriate.

The key secondary endpoints are both binary in nature and will be analysed using frequency tables, risk differences, 95% confidence intervals and p-values. The delta method and average marginal effect (AME) method will be used. In the NIV cohort, adjustment will be made for the number of days under NIV support, baseline D-Dimer level and age. For the IMV cohort, adjustment will be made for the baseline WHO value, baseline D-Dimer level and age.

For the safety endpoint (MBE to Day 6) which is binary, the Chang and Zhang exact method will be used, without adjustment for covariates.

The continuous endpoints will be analysed descriptively and inferentially, albeit in a non- confirmatory manner. A restricted maximum likelihood (REML) based ANCOVA will be used. In the NIV cohort, adjustment will be made for the number of days under NIV support, baseline D-Dimer level and age. For the IMV cohort, adjustment will be made for the baseline WHO value, baseline D-Dimer level and age. The treatment difference with 95% confidence interval will be presented.

More detailed descriptions will be provided in the TSAP.

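### The pooled major-bleeding analysis in SAP 7.5.2 has no rule for empty cells: with no SOC bleeds its interaction p-value is 1.00 whatever the data, and its interval is too narrow when alteplase bleeding is rare

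*SAP*

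**What the plan says.** Protocol 7.2.3 plans for major bleeding to Day 6 that "the Chang and Zhang exact method will be used, without adjustment for covariates" (the SAP spells the first name Chan). It states no exception for pooled cohorts, though Protocol 7.2.1 leaves combined NIV and IMV estimates to the SAP.

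SAP (Part 2) 7.5.2 keeps the exact method within each cohort: "the p-value and 95% CI will be determined using the Chan and Zhang exact method". For the pooled cohorts it changes method: "the RD 95% CI will be estimated between the two treatment arms using the same approach as for the key secondary efficacy endpoints". That approach is set out in SAP 7.5.1.2, where "the RD and 95% CI will be estimated between the two treatment arms using logistic regression, the Delta and the average marginal effect (AME) method". For bleeding, D-dimer and age are dropped ("age covariates will not be included in the model"), which leaves treatment and ventilation status.

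On homogeneity, SAP 7.5.2 says "The p-value for homogeneity will be determined similarly". In 7.5.1.2 this is the p-value of the treatment-by-ventilation interaction. The type of test is not named there, and p > 0.05 is read as homogeneous for the two key secondary efficacy endpoints.

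No fallback for cells without events appears in these sections. On Part 1, Protocol 1.1 reports: "Major bleeding events up to Day 6 were reported only in the alteplase treatment groups".

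**The concern.** Major bleeding is the only safety endpoint among the Part 2 secondary endpoints, and pooling gives the largest sample for it. The pooled method was designed for mortality and treatment failure, which the protocol expects at 9% to 40%. Major bleeding on SOC may be rare enough to leave cells empty, as it did in Part 1. A logistic model then has a coefficient with no finite estimate, and the delta method assigns an empty group a variance near zero.

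Two outputs are at stake: an interval that ignores the uncertainty in the SOC risk, and a homogeneity p-value that carries no information but lies far above 0.05.

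**Working it through.** **Inputs.** Pooled arm sizes come from the protocol synopsis: NIV about 70 SOC and 140 alteplase; IMV "up to approximately 16 patients in SOC arm and 32 in treatment arm". Pooled: 70 + 16 = 86 SOC and 140 + 32 = 172 alteplase. Part 1 SOC size: 9 patients are reported as 40.9%, so 9/0.409 = 22, with 0 major bleeds to Day 6. Part 1 high-dose size: 12 patients are reported as 60.0%, so 20. Their major bleeds number 4 in Protocol 1.1 and 3 in Protocol 1.4.2 (20% or 15%); these two statements need reconciling, but the SOC count of 0 is not affected. The documents give no expected bleeding rate or power for Part 2, so there is no stated figure to reproduce, and the SOC risks below are assumptions.

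**1. Chance of empty SOC cells,** (1 - p)^n:

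| Assumed SOC risk | 0/86 (all SOC) | 0/16 (IMV SOC) |
|---|---|---|
| 0.5% | 65% | 92% |
| 1% | 42% | 85% |
| 2% | 18% | 72% |
| 3% | 7% | 61% |

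**2. Interval with no SOC bleeds.** The treatment log-odds diverges. The estimated risk difference stays finite, at x/172, but the SOC variance tends to 0, so the interval reduces to p1 ± 1.96·√(p1(1 - p1)/172). For x = 5: p1 = 2.91%, SE = 1.28%, giving 0.4% to 5.4%. Yet 0/86 is compatible with a SOC risk of up to 1 - 0.025^(1/86) = 4.2%. Comparison, all against 0/86:

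| Alteplase | Planned (delta/AME) | Miettinen-Nurminen score | Chan-Zhang exact |
|---|---|---|---|
| 5/172 (2.9%) | 0.4% to 5.4% | -1.4% to 6.6% | -1.8% to 6.8% |
| 9/172 (5.2%) | 1.9% to 8.6% | 0.9% to 9.7% | 0.2% to 9.7% |
| 17/172 (9.9%) | 5.4% to 14.3% | 5.5% to 15.3% | 4.1% to 15.4% |
| 26/172 (15.1%) | 9.8% to 20.5% | 10.5% to 21.2% | 9.9% to 21.4% |
| 34/172 (19.8%) | 13.8% to 25.7% | 14.5% to 26.4% | 14.1% to 26.5% |

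At 5/172 the planned interval excludes zero and the other two do not. Its width is 5.0 points against 8.1 for the score interval. At 26/172 both are 10.7 points wide.

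**3. Interaction with no SOC bleeds.** Take alteplase 7/140 in NIV and 10/32 in IMV. The model without interaction already fits all four cells exactly, because both SOC risks go to zero and ventilation status fits the two alteplase risks. Adding the interaction therefore cannot improve the fit: p = 1.00 by likelihood ratio and by Wald. The risk differences are 5 points (exact interval -1.1% to 10.1%) and 31 points (5.3% to 50.0%). Any other split of the alteplase bleeds gives the same p.

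**4. Interaction with only the IMV SOC cell empty.** Alteplase is again 7/140 (NIV) and 10/32 (IMV), and IMV SOC is 0/16.

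- NIV SOC 1/70: Wald SE about 12,000, p = 0.999; likelihood-ratio p = 0.15.
- NIV SOC 3/70: likelihood-ratio p = 0.019.
- NIV SOC 1/70 with one event placed in the empty cell (IMV SOC 1/16): likelihood-ratio p = 0.68.

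Here the outcome depends on the test used.

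**The case against.** The strongest reply has five parts.

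- **The interval.** A reader might infer that the planned interval is too narrow whenever SOC has no bleeds. The documents do not support that: the only alteplase rate they give for this dose is 15% to 20%, and there the planned and score intervals are equally wide. Narrowness needs a lower rate. Part 2 adds measures against bleeding, so a lower rate is plausible, but no document states one. Over all outcomes the delta interval covers 92% to 95%. Given zero SOC bleeds, coverage falls to 74% to 93% at a true SOC risk of 2% and 24% to 87% at 3% (alteplase 3% to 20%), and the exact method is itself conservative.
- **The empty IMV cell.** A reader might infer that this alone makes the homogeneity result automatic. That assumes a Wald test. SAP 7.5.1.2 and 7.5.2 name none; Wald is specified for the Cox model in 7.4.1. A likelihood-ratio test stays usable and can detect heterogeneity, as the 3/70 case shows.
- **Scale and power.** The 0.68 above, with no cell empty, shows that part of the problem is an odds-ratio test with 16 SOC patients.
- **Reporting.** A reader might infer that an empty cell would be reported as proof that both cohorts bleed alike. The p > 0.05 rule is worded for the key secondary endpoints and reaches bleeding only through the word similarly. Protocol 7.2.5 plans no hypothesis testing for safety.
- **Importance.** The pooled analysis is exploratory. The cohort analyses keep the exact method, and NIV alone supplies about 210 of 260 patients. A lower limit above zero errs towards signalling harm.

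All five limit the point. They do not justify the pooled method: with no SOC bleeds the interaction p is 1.00 under either test, and the planned upper limit is also too low (5.4% against 6.6% at 5/172), which understates the largest plausible excess.

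**Conclusion.** The point holds in a limited form. The pooled bleeding analysis has no rule for a foreseeable data pattern. With no SOC bleeds at all, the treatment coefficient is not estimable, the interaction p is 1.00 regardless of the cohort risks, and the interval leaves out SOC uncertainty. That narrows the interval materially at alteplase risks of about 3% to 5% and hardly at all at 15% to 20%. With only the IMV SOC cell empty, the p-value is uninformative if it is a Wald p-value; otherwise the test is usable but weak.

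The chance of complete failure, 65% to 7%, rests on assumed SOC risks of 0.5% to 3% and on the IMV cohort filling to its cap. A smaller IMV cohort makes empty cells likelier. The homogeneity p-value is the firmer half of the point. The confirmatory results and the cohort-level exact bleeding results are not touched, so this is a change worth making before the snapshot, not a threat to the trial's conclusions.

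**What to change.** In SAP 7.5.2:

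- Estimate the pooled major-bleeding risk difference as a Mantel-Haenszel difference stratified by ventilation status with a Miettinen-Nurminen score interval, or use the exact method already planned for the cohorts. Both remain defined with empty cells, and the stratified estimate fits the combined-estimate approach that Protocol 7.2.1 leaves to the SAP.
- Replace the homogeneity p-value for bleeding by the two cohort risk differences side by side with their exact intervals, which are already planned.
- If a p-value is still wanted, name an exact test or a Firth-penalised interaction test, and state that p > 0.05 is not read as homogeneity.

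The cost is a few lines of SAP text and standard software options. No new data are needed.
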